Gabapentin is clinically started at a low dose and increased until either effectiveness is demonstrated or an upper limit dose, derived empirically, is reached. Based on work by [name] and Solodiuk we have established a dose titration schedule that will reach a typically effective dose over 15 days ([name], personal communication).⁴⁴ Extensive expert opinion shows that in the setting of children with neurological irritability and pain, as opposed to functional chronic pain in other children/youth, the onset of pain relief is much more rapid than several weeks. Ref. 49 describes improvement in pain scores (NPASS) in a neonatal cohort at 14 days. In another study, an RCT of gabapentin in children, a stable dose was reached at 22 days, and clinical effect was seen within that time frame, even though the protocol continued to 30 days. [Effectiveness of Gabapentin on Chronic Irritability in Neurologically Impaired Children. ClinicalTrials.gov Identifier: NCT01675960. The trial was terminated due to slow recruitment (2 enrolled)]. In personal communication with the study PI, ([name]), most of the effect was actually within 2 weeks and this is confirmed in his clinical practice. [name], author of Ref 41, 43 and 44 concurs with this time frame, in personal communication. Parent-caregivers will administer either active gabapentin or placebo on the same schedule. When transitioning between gabapentin and placebo, in either direction, there will be a 3-day washout period. A study dosing table is shown in Section 3 3

The primary variable assessed is the child's pain score. Pain and irritability will be measured using the Non-Communicating Children's Pain Checklist – Revised (NCCPC-R) at specified intervals throughout the randomized sequence of G: P. Additional measures of parent/caregiver burden and impact on their daily function will be undertaken weekly with the PROMIS-57, a tool adapted to measure the impact of the child's pain and irritability on parental functioning. This multi-dimensional tool assesses the parent/caregiver's stress, activity, function and sleep and is a proxy for the distress caused by the child's condition.

Other measures will be of usual, known side effects (e.g., sedation) and of any unexpected adverse events. Known side effects will be assessed regularly at the start, mid-point and end of each sequence via the Health Update. Unexpected adverse events will be tracked continuously.

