Summary: This study uses a rapid and safe dose escalation to the widely accepted therapeutic range where evaluation of response will be undertaken with frequent scoring. Different maximal doses are used for children < or ≥ 15 kg, based on pharmacokinetic data. Doses are titrated to clinical effect or maximum target dose, whichever is lower. Once in the therapeutic range, doses change after 3 days if there is not an adequate reduction in symptoms. For any subject that obtains clinical benefit below maximal dose, then they will be held at that dose for the remainder of that period until such time as the scheduled wean begins. At the end of each treatment period there is a wash-out.

Starting Dose: The starting dose of gabapentin will be 5 mg/kg administered as oral liquid or via gastric or jejunal routes. On Day 1 of the study, the gabapentin will be administered once at bed-time and then increased according to the schedule shown in Table 1.

Dose Escalation: The dose will be increased every 3^{rd} - 4^{th} day in a step wise fashion of 13% - 50%, starting with the evening dose in order to accommodate sedation. The maximum dose for subjects will be as follows: < 15 kg to 60 mg/kg day and \geq 15 kg to 45 mg/kg/day. Dose titration will be to a maximum target dose (based on weight as described, < 15 kg, > 15kg) or to clinical effect, whichever is lower. The dose escalation scheme is based upon expert consensus and personal communication with [name], [name], and upon review with the BC Children's Hospital research pharmacist. \cdot , 56.

Some children with PIUO and SNI have been given gabapentin empirically by their health care provider, often without any subsequent, detailed assessment of benefit. Many times, the medication is continued because of its low side-effect profile and overall safety compared with other analgesics. If a subject is currently on gabapentin at the time of enrolment, and the parent/caregiver wants an evaluation of its effectiveness, then the subject can be enrolled in this study with the following approach:

After appropriate enrolment and consent, the subject will be weaned off of gabapentin, in a stepwise manner with 25% reductions in dose every 3rd day. Once they are no longer on the active drug, they will be randomized to active drug or placebo like all other study participants.

Gabapentin Risks and Precautions

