3.8. Trial Procedures and Evaluations

Screening

Screening will be performed prior to the Baseline Visit as a preliminary assessment of the participant's eligibility. Screening will take place over the phone. The researchers will explain the study to the prospective participant in lay terms, including possible side effects of the therapy. The researchers will use the Eligibility Assessment to confirm whether the prospective participant is eligible. The Eligibility Assessment includes confirmation of the prospective participants':

- Age (must be between 3 and 18 years old)
- GMFCS level (must be 3, 4 or 5)
- CFCS level (must be 4 or 5)
- Pain Score (must be 3 or higher)*
- Pain Identification (must be PIUO, evidenced by a score of 3 or higher)*
- * A Pain Score of 3 refers to the eligibility screening for the PIUO study, which potential participants may have participated in. The eligibility screening for the PIUO study includes a score to identify the pain as PIUO and a score to measure the persistence and distress level of the pain congruent with the Pain Survey scores of C, D, or E. In the eligibility screening these components are numerical scores.

If eligible, the prospective participant will be provided with the Consent Form. Upon receiving the signed Consent Form the researchers will schedule a Baseline Visit. Prior to the Baseline Visit the researchers will collect data from all medical records to fill out the Health Information Form. The data collected will be confirmed with the participant at the Baseline Visit. The participant will also receive the Demographic Information, the NCPCC-R and the POMIS-57 to complete immediately prior to the Baseline Visit.

Some children will already have completed evaluation via the PIUO Pathway, either as part of our current, ongoing study of children with PIUO, or by their primary provider who has used the PIUO

Pathway approach. These children will not need to undergo re-evaluation, but can move directly to the gabapentin trial.

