If a subject who otherwise meets inclusion criteria has not undergone the evaluation for treatable, nociceptive-inflammatory causes of pain and irritability described by the PIUO Pathway, then we will conduct a PIUO Pathway evaluation first. If a treatable cause is identified, then the child will be referred back to their primary health care provider, and will not be enrolled in the gabapentin trial. If no treatable cause is found, then the child may continue onto the gabapentin trial. It is expected that undertaking a full PIUO Pathway evaluation may take 2-4 weeks time.

Baseline Visit

The Baseline Visit will be in person and will last approximately 2 hours. The following activities will be conducted prior to drug dispensing:

- Medical history: The participant will be asked to confirm findings in the Health Information Form. The following clinical information will also be collected for each participant:
 - o Any pre-existing medical conditions/signs/symptoms as part of the medical history.
 - o List of concomitant medications, dosage and date of treatment initiation
- Vital signs: Seated blood pressure (BP), heart rate (HR), respiration rate, oxygen saturation (SpO2), temperature, weight and height will be recorded.
- A head to toe physical exam will be performed
- The participant will be asked to complete the following at the Baseline Visit:
 - o Demographic Information (Appendix 3)
 - o Pain Survey (Appendix 5)
 - o NCPCC-R (Appendix 7)
 - o PROMIS-57 (Appendix 8)

In addition to reviewing all previous clinical work-up related to pain and irritability, we will establish a baseline for participants' expectations to the effectiveness of gabapentin. Pain is highly modifiable by psychological factors such as beliefs and expectations, which may influence treatment response (via placebo analgesia). This is especially important in this context of children with SNI where caregivers play a key role in assessment and management of pain and a placebo-by-proxy effect might occur based on the parents' perceptions/behavior. To evaluate the Impact of Expectations all families will be asked at the Baseline Visit if they expect participation in the trial will be of benefit to their child and at Follow Up they will be asked if the trial was of benefit to them and/or their child. They will also be asked after each sequence whether they believe their child received medication or placebo.

Randomization

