6.2. Schedule of Enrolment, Interventions, and Assessments

Gabapentin Trial Diagrams and Summaries

Table 3 shows which assessments happen during specific phases of the trial. Table 4 shows the exact timepoint assessments are administer

Trial Design Summary

- Repeated Measures Single Cross-Over Trial (Treatment and Placebo)
- We will recruit 10 study participants. These participants will have completed the PIUO Pathway without resolution of pain. They will have severe neurological impairment and unexplained, untreated pain.
- The study participants will be randomized to treatment or placebo arms. This first session will take 25 days. During this time the treatment arm gabapentin dose will be slowly increased until an effective dose or maximum dose (60mg/kg/day) is reached, whichever comes first.
- The participants will then undergo a three-day long washout period, where neither drug nor placebo will be administered.
- Following this, the participants that were on placebo previously will switch to gabapentin treatment and those who were on gabapentin treatment will switch to placebo. This will again go on for 25 days, with the gabapentin dose increasing throughout.
- NCCPC-R, PROMIS-57 and Pain Surveys will be administered throughout the trial to obtain data
- The total participant time will be around 55 days.
- The diagram below depicts the Gabapentin trial design.

N-of-1 Design

The Gabapentin Trial will use an N-of-1 design. This means that each participant will be his or her own experiment, acting as both treatment and placebo participants. In an N-of-1 trial, each participant's treatment data is compared to his or her own placebo data, and the results are specific to

the individual participant. A small "N" such as 10 (as we are going to recruit for the Gabapentin Trial) can provide an adequate amount of data when using an N-of-1 design because 10 separate data sets and results will be produced. Multiple N-of-1 trials that are conducted on similar patients taking similar drugs can be amalgamated to give broader results.

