N-of-1 trials allow for the development of personalized medicine, which is ideal when working with a population of high heterogeneity, such as children with severe neurological impairment. Each of the participants will be unique in his or her own physical and emotional health needs. An N-of-1 trial allows the researcher to determine if treatment is effective in a specific individual, as well as the optimal dose, tolerability and potential side effects of the treatment for that individual. A standard cross-over trial may elicit the answer to the question of "Does drug X relieve pain in children with severe neurological impairment?" but an N-of-1 trial can answer the question of "Does 10mg/kg of drug X relieve pain in a 10-year-old female whose severe neurological impairment is caused by Rett Syndrome?".

The diagram below depicts a sample N-of-1 trial with five participants. Each colour represents an individual participant, and their cause of severe neurological impairment is listed on the right. Each participant will trial the treatment (in our case Gabapentin) and the placebo, in randomized order. The results (check mark = pain resolved and "X" = pain not resolved) are also coloured in to show that the results are specific to the individual. For example, the treatment that worked for the participant with Rett Syndrome may have been 30 mg/kg/day of drug X, while the effective treatment for the participant with cerebral palsy may have been 15mg/kg twice a day, because he/she was overly sensitive to the sedative effects of drug X and required a lower dose.

[figure not shown]

Table 3: Gabapentin Trial Events Schedule

Study Phase	Screening and Enrollment	Baseline Visit	Sequence 1	Study Visit	Sequence 2	Study End	Follow Up
Study Time Point	- 4 to 0 weeks	Day 1 of Period 1	Day 1 – 26 of Period 1	Day 1 of Period 2	Day 1 – 26 of Period 2	Day 26 of Period 2	1 week post Study End
Eligibility Assessment	X						
Informed Consent	X						
Demographic Information		X*					
Health Information Form		X*					
Medical History		X*					
Physical Exam		X*					
Pre-Participation Questionnaire		X					
Randomization		X					
Study Drug Dispensing		X		X			
Pain Survey			X		X	X	
NCCPC-R			X		X	X	
PROMIS-57			X		X	X	
Adverse Events Log			X		X	X	

Version 3.0 October 4, 2020 Page 38 of 45

Health Update		X		X	X	
Concomitant Medications		X		X	X	
Study Drug Accountability			X		X	
Participation Questionnaire						X

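### Children weaned off their own gabapentin can be randomized and baseline-scored as soon as dosing stops, with no drug-free interval, although the trial sets 3 days at the period switch; only the lowest-effective-dose outcome is clearly exposed.

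*Protocol*

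**What the plan says.** Protocol section 3.3 (Dose Escalation) admits children already on gabapentin if the family wants the drug evaluated. After consent the child is weaned "in a stepwise manner with 25% reductions in dose every 3rd day". Then: "Once they are no longer on the active drug, they will be randomized to active drug or placebo like all other study participants". Neither this section nor any other sets a minimum time off drug before randomization.

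The baseline score is tied to the randomization visit. Section 3.8 (Screening) says: "The participant will also receive the Demographic Information, the NCPCC-R and the POMIS-57 to complete immediately prior to the Baseline Visit". The Baseline Visit list in the same section, introduced by "The following activities will be conducted prior to drug dispensing", includes the NCCPC-R. Table 3 (section 6.2) dates the Baseline Visit "Day 1 of Period 1" and marks randomization and drug dispensing in that column.

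Between periods the rule differs. Section 2.3: "When transitioning between gabapentin and placebo, in either direction, there will be a 3-day washout period". Section 6.2: "The participants will then undergo a three-day long washout period, where neither drug nor placebo will be administered".

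Section 3.10 defines the lowest effective dose as the smallest dose giving at least an 11-point NCCPC-R reduction from baseline, without rebound over 3 days, within days 11-19 on active drug. Baseline is not pinned to a particular score. The primary outcome (section 3.4) contrasts days 11-19 on gabapentin with the same days on placebo.

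**The concern.** A baseline should describe the child off drug and settled. For a prior user, the text allows it to be taken when the drug has only just stopped. Two things could distort it, in opposite directions:

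- Remaining relief from the drug would lower baseline and could hide a real 11-point drop.
- A rise in symptoms after stopping would raise baseline and could make a low trial dose look effective.

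The lowest effective dose serves the protocol's first secondary objective, optimal dosing. Prior users are invited precisely because their families want to know whether the drug works. The trial already applies a 3-day standard when a child changes from one treatment to the other, and the entry of prior users has no counterpart.

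**Working it through.** The protocol gives no figure of its own to reproduce here. The check sets the rules side by side and then sizes the residual drug.

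**Inputs**
- Half-life 5-7 h (section 2.1, Treating with Gabapentin).
- Wean in 25% steps every third day (section 3.3).
- Washout of 3 days between periods (sections 2.3 and 6.2).
- Threshold of 11 points from baseline (section 3.10).
- Screening window of 4 weeks, or 28 days (Table 3).
- PIUO Pathway evaluation of 2-4 weeks, or 14-28 days (section 3.8).

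**1. Required drug-free days.** Before period 1 for a prior user: 0 stated. Between periods: 3. For a child who was in the PIUO Study within the last 6 months, the Table 3 footnote asks only for a Health Update before dispensing, so no other step enforces a delay. Baseline can therefore fall within about a day of the last weaning dose.

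**2. Residual drug.** Assume first-order elimination and a last weaning level of 25% of the original. Share of the original level left after h hours = 0.25 × 2^(−h / half-life).

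| Hours | Half-life 5 h | Half-life 7 h |
|---|---|---|
| 12 | 0.25 × 0.189 = 4.7% | 0.25 × 0.305 = 7.6% |
| 24 | 0.25 × 0.036 = 0.9% | 0.25 × 0.093 = 2.3% |
| 72 | 0.25 × 0.00005 = 0.001% | 0.25 × 0.0008 = 0.02% |

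**3. Does the wean reach zero?** With steps of the original dose, the levels are 75, 50, 25 and 0%. With steps of the current dose, the level after n steps is 0.75^n: 31.6% after 4 steps, 10.0% after 8, 3.2% after 12, and never zero. The text does not say which is meant, so on the second reading the moment at which the child is off drug is not fixed.

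**4. Which outcomes use baseline B?**
- Lowest effective dose: the score must fall to B − 11. If B is shifted by s, the target becomes B + s − 11, a one-for-one shift.
- Maximal-effect dose and latency: the day or dose with the largest B − Y. Adding s to every difference leaves the maximum in the same place.
- Primary outcome: mean score over days 11-19 on gabapentin against placebo. B does not appear. By day 11 at least 10 × 24 = 240 h have passed since the wean ended, or 240 / 7 = 34 half-lives at the slower rate.

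**5. Which children?** If the Baseline Visit score is baseline throughout, all prior users are exposed. If each period's own day 1 score is baseline, only prior users randomized to gabapentin first are.

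**6. Does a 3-day interval fit?** A four-step wean takes 9-12 days, depending on when the first reduction is counted. Adding 3 gives 12-15 days, within 28. Done in sequence with the Pathway, the total is 12 + 14 = 26 to 15 + 28 = 43 days, which can exceed 28.

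**The case against.** The strongest case against is that no harm is shown. Residual drug is nearly gone in a day, and the protocol nowhere says that stopping gabapentin disturbs NCCPC-R scores. Three days is more than clearance needs and is not shown to be enough for symptoms to settle. The washout rule was written for the switch between treatments, where carryover could reach the other arm. The text permits immediate scoring but does not require it, and an in-person visit has to be scheduled. All of this stands, and it keeps the point small. It does not remove the gap: the entry rule still allows a baseline taken barely off drug, and the trial has a ready standard to borrow.

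Three stronger readings are tempting but unsupported.

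- A reader might infer a breach of the washout rule. Sections 2.3 and 6.2 govern only the change between treatments, so this is an uneven standard and not a contradiction.
- A reader might infer that prior users stop more abruptly, from 25% of their dose against 5/60 = 8.3% or 75/675 = 11.1% at the end of a trial period. That holds only for trial children at maximum dose and only if wean steps are of the original dose. Section 3.3 holds responders at lower doses. If a child held at 20 mg/kg/day followed the tabulated last step, it would be 5/20 = 25%, the same.
- A reader might infer bias in the primary result or in the titration itself. The primary contrast does not use baseline, and section 3.3 does not say against what an adequate symptom reduction is judged.

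**Conclusion.** The point holds as a limited gap in the entry rule for prior users. Zero drug-free days are required before their baseline score, against 3 at the period switch. Residual drug is about 5-8% of the original level at 12 hours and 1-2% at 24 hours, assuming first-order elimination and a last step of 25% of the original dose. Any symptom change after stopping cannot be sized from the protocol, in amount, direction or duration.

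The clear exposure is one secondary outcome, the lowest effective dose, which is only summarized descriptively. It matters only where the shift moves the 11-point crossing to another dose step. It concerns prior users only, an unstated number among 10 that may be zero, and fewer still if each period has its own baseline. Who counts as having benefited is touched only if the 11 points in section 3.4 are also read as measured from baseline. The primary comparison is not affected. This is worth a cheap correction and does not threaten the trial's main conclusion.

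**What to change.** In section 3.3, where the wean is described:

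1. State that each 25% step is of the original dose, so the wean ends at zero on a known day.
2. Require at least 3 drug-free days after the last weaning dose before the baseline NCCPC-R and the first day of period 1, matching the trial's own washout. Three days is offered for consistency; the protocol does not show that symptoms have settled by then.

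The cost is a sentence or two of text and about 3 more days off drug for children in pain, ahead of a trial in which every child already has a 25-day placebo period. The wean and interval fit the screening window for children who have completed the PIUO Pathway. For the others, section 3.8 notes: "It is expected that undertaking a full PIUO Pathway evaluation may take 2-4 weeks time". For them the wean would run alongside the Pathway, or the screening window would be extended.

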Risk minimization, management, and assessment procedures have been implemented in the study to minimize and assess potential risks to participants who participate in this clinical study with gabapentin. Components include: (1) specific study eligibility and exclusion criteria to ensure that participants who have underlying characteristics that potentially increase their risk for an adverse outcome are excluded. These include patients with a history of previous sensitivity to gabapentin. (2) Protocol-specific procedures for minimizing and managing AEs: sedation is the most common AE to gabapentin, and we will address this by titrating upwards on the dose every 3rd day, and always increasing the nighttime dose first; (3) overview surveillance by the independent Data Safety Monitoring Board; (4) ongoing follow-up throughout the study by research personnel twice weekly, coinciding with dose increases to check for AE as shown in the table below.

Refer to the TEVA-Gabapentin (gabapentin) TEVA Canada Product Monograph (DIN 02244515) for a detailed description of warnings, precautions, and adverse events: https://health-products.canada.ca/dpd-bdpp/info.do?lang=en&code=68492

The following potential side effects occurred in clinical trials across ages 3-adults at rates higher than in placebo groups:

- Somnolence
- Dizziness
- Fatigue
- Nausea and/or Vomiting
- Increase Weight
- Emotional Lability
- Hostility
- Hyperkinesia
- Respiratory Infection
- Fever
- Swelling of limbs
- Gait disturbance

Implementation and adherence

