The risk of serious side effects of respiratory depression with concomitant use with opioids is acknowledged (BC Children's Hospital Integrated Pain Service Gabapentin Information http://www.bcchildrens.ca/Pain-Services-Site/Docu-Sheet. Accessed at: ments/BCCH1455Gabapentin.pdf. Retrieved on October 4, 2020). A minority of patients might be on opioids. Dose adjustments will be added when gabapentin is used with a concomitant opioid or other CNS depressant medication: the family will be advised to return to the previous stable, safe dose in the protocol, and the subject will remain at that dose with no further escalation for the duration of the trial arm. This schedule will be duplicated on the parallel arm (active drug or placebo) to maintain masking. The participants are highly monitored, often with continuous oxygen saturation monitoring and/or "baby-cam" devices observing them during sleep. During the daytime they are with family, or professional caregivers (aides, nurses, etc.). These individuals will be advised to watch for respiratory depression and sedation that occur well before fatal apnea, and how to respond.

While there are no prohibitions on concomitant care, any care or medications unrelated to the trial will be noted in the CRFs for each participant.

Participants are sometimes obtaining respite care at facilities with nursing and physician care. Medical reconciliation is done at each admission. Parents will be provided with a letter to share with these programs outlining the study, the drug being tested, and a 24-hour pager to contact for further information or concerns

Active Participants < 15kg in mg per kg

Day	Morning mg/kg	Noon mg/kg	Evening mg/kg	Total mg/kg per day	% Change
1*	0	0	5	5	0
2	0	5	5	10	100%
3	5	5	5	15	50%
4	5	5	5	15	0%
5	5	5	10	20	33%
6	5	5	10	20	0%
7	5	5	10	20	0%
8	10	10	10	30	50%
9	10	10	10	30	0%
10	10	10	10	30	0%
11	13.3	13.3	13.3	40	33%
12	13.3	13.3	13.3	40	0%
13	13.3	13.3	13.3	40	0%
14	17	17	17	50	25%
15	17	17	17	50	0%
16	17	17	17	50	0%
17	20	20	20	60	20%
18	20	20	20	60	0%
19	20	20	20	60	0%
20	13.3	13.3	13.3	40	-33%
21	6.7	6.7	6.7	20	-50%
22	0	5	5	10	-50%
23	0	0	5	5	-50%
24	0	0	0	0	-100%
25	0	0	0	0	0%
Switch over*	-	-	-	-	-

^{*}Day one or 26 if switching over, not both.

Active Participants > = 15kg in mg per day

Day	Morning mg	Noon mg	Evening mg	Total mg/kg per day	Total mg/day	% Change
1*	0	0	75	5	75	0
2	0	75	75	10	150	100%
3	75	75	75	15	225	50%
4	75	75	75	15	225	0%
5	100	100	100	20	300	33%

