6	100	100	100	20	300	0%
7	100	100	100	20	300	0%
8	150	150	150	30	450	50%
9	150	150	150	30	450	0%
10	150	150	150	30	450	0%
11	200	200	200	40	600	33%
12	200	200	200	40	600	0%
13	200	200	200	40	600	0%
14	225	225	225	45	675	13%
15	225	225	225	45	675	0%
16	225	225	225	45	675	0%
17	225	225	225	45	675	0%
18	150	150	150	30	450	-33%
19	150	150	150	30	450	0%
20	100	100	100	20	300	-33%
21	100	100	100	20	300	0%
22	50	50	50	10	150	-50%
23	25	25	25	5	75	-50%
24	0	0	0	0	0	-100%
25	0	0	0	0	0	0%
Switch over*	_	-	-	-	_	-

^{*}Day one or 26 if switching over, not both.

Inactive

Day	Morning mg/kg	Noon mg/kg	Evening mg/kg	Total mg/kg per day	% Change
1*	0	0	0	0	0%
2	0	0	0	0	0%
3	0	0	0	0	0%
4	0	0	0	0	0%
5	0	0	0	0	0%
6	0	0	0	0	0%
7	0	0	0	0	0%
8	0	0	0	0	0%
9	0	0	0	0	0%
10	0	0	0	0	0%
11	0	0	0	0	0%
12	0	0	0	0	0%
13	0	0	0	0	0%
14	0	0	0	0	0%
15	0	0	0	0	0%
16	0	0	0	0	0%
17	0	0	0	0	0%
18	0	0	0	0	0%
19	0	0	0	0	0%
20	0	0	0	0	0%
21	0	0	0	0	0%
22	0	0	0	0	0%
23	0	0	0	0	0%
24	0	0	0	0	0%
25	0	0	0	0	0%
Switch over*	0	0	0	0	0%

^{*}Day one or 26 if switching over, not both.

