3.4. Outcomes

1. Primary Outcome: The mean pain and irritability score on the NCCPC-R through days 11-19 on active drug compared to placebo.

[figure not shown]
An 11-point decrement in the NCCPC-R score with no rebound x 3 days is considered clinically meaningful minimum change (improvement).

Secondary Outcomes:

- 2. For patients who benefited from gabapentin, identification of the lowest dose that was effective in reducing pain scores, as shown by a improvement the NCCPC-R score compared to baseline during day 11-19 on active drug.
- 3. For patients who benefited from gabapentin, identification of the maximal effect dosage as measured by the largest improvement in the NCPCC-R score compared to baseline during days 11-19 on active drug.
- 4. Identification of the latency time in days to the onset of maximum relief of pain and irritability as measured by the NCCPC-R score over days 0-19.
- 5. Adverse Events Collection demonstrates the AE on treatment arm do not exceed the frequency found in the Product Monograph for children receiving gabapentin.
- 6. Exploratory Outcome: PROMIS-57 scores reported by parent/caregiver are improved on the treatment arm compared to the placebo arm.

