Should a clinically significant AE occur, the Study Medical Monitor will be notified. The monitor will require unblinding by the study pharmacist. The Investigator will be advised by the Medical Monitor and review with the parent/caregiver. Modifications may need to be made in the study sequence, for example, extending the time between dose increases. Any modifications in the protocol will be reflected on both the gabapentin and placebo arms.

Any AE that occurs between the time that a study participant is enrolled and the time that s/he departs the study at the end of the final study visit (or at the time of early discontinuation of the participant from the study for any reason) will be captured and recorded. At each contact with the participant, the investigator (or designate) must seek information on AEs by specific questioning and, as appropriate, by examination.

AEs that have been reported by the study participant will be followed-up for duration, intensity and possible recurrence.

All AEs (including SAEs) will be followed until resolution or until the investigator and the Medical Monitor agree that the AE has resolved, stabilized or become chronic and no further follow-up is required.

In the case of a Suspected Unexpected Serious Adverse Reactions (SUSARs) the Sponsor will expedite the reporting of the event to investigator(s), institutions(s), ethics board(s), and Health Canada per published guidelines. If the adverse reaction is not documented in the Product Monographs (new occurrence) and is thought to be related to the study treatment, the study sponsor may urgently require further information from the investigator for regulatory reporting.

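### The sedation safeguard of raising the night dose first is not carried into the dosing tables from day 5 (15 kg and over) or day 11 (under 15 kg)

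*Protocol*

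**What the plan says.** Section 3.3, Gabapentin Risks and Precautions, lists the measures that limit adverse events. For sedation it says: "we will address this by titrating upwards on the dose every 3rd day, and always increasing the nighttime dose first". The Dose Escalation paragraph of the same section describes increases "in a step wise fashion of 13% - 50%, starting with the evening dose in order to accommodate sedation", and the Starting Dose paragraph refers to Table 1 for the schedule.

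The tables list morning, noon and evening doses for each day. Under 15 kg (mg/kg; day, three doses, total, percent change) the day 11 row reads "11 13.3 13.3 13.3 40 33", after 10/10/10 on day 10. At 15 kg and over (mg; day, three doses, mg/kg total, mg total, percent change) the day 8 row reads "8 150 150 150 30 450 50", after 100/100/100 on day 7.

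Parents or caregivers give the drug at home, guided by a daily tracker and the pharmacist's instructions (section 3.3, Implementation and adherence).

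**The concern.** The risk section promises that the night dose is always raised first. If the tables raise all three doses on one day, the child meets the new level in the morning, while awake, and the stated measure is absent at that step. An ethics board or safety board weighing the risk section would credit a protection that the operative schedule does not give. The participants have limited communication, most are expected to be on other medication, and a minority may be on opioids (section 3.3, Concomitant Care).

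**Working it through.** **Inputs.** The two active dosing tables in section 3.3. A step departs from the rule if a morning or noon dose rises above the evening level already reached on an earlier day.

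**Change at each increase after day 1 (morning/noon/evening)**

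| Day | 15 kg and over, mg | Under 15 kg, mg/kg |
|---|---|---|
| 2 | 0/+75/0 | 0/+5/0 |
| 3 | +75/0/0 | +5/0/0 |
| 5 | **+25/+25/+25** | 0/0/+5 |
| 8 | **+50/+50/+50** | +5/+5/0 |
| 11 | **+50/+50/+50** | **+3.3/+3.3/+3.3** |
| 14 | **+25/+25/+25** | **+3.7/+3.7/+3.7** |
| 17 | none | **+3/+3/+3** |

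Bold marks the joint steps. Days 1-3 build up evening, then noon, then morning in both tables, so they comply. Under 15 kg, day 5 raises the evening alone (5/5/10) and day 8 brings the daytime doses up to it (10/10/10), so these comply too.

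**Can the rows mean an evening start?** No. The printed totals include all three raised doses. At 15 kg and over on day 5, 3 x 100 = 300 mg, as printed; an evening-only start would give 75 + 75 + 100 = 250. Under 15 kg on day 11, 3 x 13.3 = 39.9, printed as 40; an evening-only start would give 10 + 10 + 13.3 = 33.3.

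**Share of the escalation, if taken to the maximum**
- 15 kg and over: 4 of 6 increases; 75 + 150 + 150 + 75 = 450 of 675 - 75 = 600 mg/day (75%).
- Under 15 kg: 3 of 7 increases; 3 x (3.3 + 3.7 + 3) = 30 of 60 - 5 = 55 mg/kg/day (55%).
- Two thirds of the joint rise falls on morning and noon: 300 of 450 mg/day, and 20 of 30 mg/kg/day.

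**Size per dose.** At 15 kg and over, joint rises are 25 or 50 mg against 75 mg on days 1-3. At exactly 15 kg that is 25/15 = 1.7 or 50/15 = 3.3 mg/kg, and less in heavier children. Under 15 kg, they are 3 to 3.7 mg/kg against 5 mg/kg in the early steps.

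**Contacts.** Table 4 (section 6.2) has an NCCPC-R assessment on days 5, 8, 11, 14 and 17, so every joint step has one. Day 11 also has the Health Update.

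**The case against.** The strongest reply is that one overbroad word is at issue. The tables stand in the same section as the promise, dosing is referred to them, and no dose is ambiguous, so rewording would be enough. Further protections remain. Follow-up is twice weekly and timed to dose increases (section 3.3, Gabapentin Risks and Precautions; section 3.8, Study Contacts). With an opioid or other CNS depressant, "the family will be advised to return to the previous stable, safe dose in the protocol" and escalation stops. After a clinically significant event the plan allows "extending the time between dose increases" (section 3.12), and section 4.2 allows slower titration for minor side effects. Also, "Doses are titrated to clinical effect or maximum target dose, whichever is lower", so a child who responds early meets fewer joint steps.

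Most of this stands, and it limits the weight. It does not make the promise true. Rewording alone would also leave the trial without a measure that its own risk section relies on.

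Three stronger readings are tempting, and the documents support none of them.
- A reader might infer that the schedule is unsafe, or that 75% and 55% measure sedation risk. They are shares of the dose added. Nothing in the protocol shows that a joint step sedates more than a split one.
- A reader might infer that caregivers will not know which dose to give. The tables and tracker settle that.
- A reader might infer that the Dose Escalation paragraph is contradicted just as plainly. Its phrase about the evening dose can be read as describing only the start of titration. The clear conflict is with the unconditional rule in the risk paragraph.

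**Conclusion.** The contradiction holds. At four steps for children of 15 kg and over and three for those under 15 kg, the tables raise the morning dose before the evening dose, so the stated sedation safeguard is not delivered there. The shares of 75% and 55% assume escalation to the maximum dose as tabled. The safety weight is modest, given the smaller rises per dose, the assessment on each joint-step day and the other protections. No endpoint or analysis is wrong as a result. It should still be corrected before drug is dispensed, because a safety rule and the schedule meant to carry it out disagree.

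**What to change.** In the tables and daily tracker, begin each joint step with the evening dose of the listed day and raise morning and noon the next day. The table for children under 15 kg already does this in part on day 5. Mirror the change in the placebo schedule to keep the masking.

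| Day | 15 kg and over, mg (total, was) | Under 15 kg, mg/kg (total, was) |
|---|---|---|
| 5 | 75/75/100 (250, was 300) | unchanged |
| 8 | 100/100/150 (350, was 450) | unchanged |
| 11 | 150/150/200 (500, was 600) | 10/10/13.3 (33.3, was 40) |
| 14 | 200/200/225 (625, was 675) | 13.3/13.3/17 (43.6, was about 50) |
| 17 | no step | 17/17/20 (54, was 60) |

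Each step stays on its contact day. Each non-final level reached and left by a joint step still lasts nine doses: 1 + 3 + 3 + 2.

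**Costs**
- Exposure falls slightly in the primary window, defined as "The mean pain and irritability score on the NCCPC-R through days 11-19 on active drug compared to placebo". At 15 kg and over the tabled sum for days 11-19 is 3 x 600 + 4 x 675 + 2 x 450 = 5,400 mg; the loss is 100 + 50 = 150 mg (2.8%). Under 15 kg, from the printed doses, the sum is 3 x (39.9 + 51 + 60) = 452.7 mg/kg; the loss is 6.6 + 7.4 + 6 = 20 mg/kg (4.4%).
- The top level lasts seven doses instead of nine under 15 kg, and ten instead of twelve at 15 kg and over.
- The step days become mixed. State how they count for the lowest effective and maximal effect doses, for example at the lower level, which two of the three doses follow.
- The change is an edit to tables and tracker, with ethics approval of the modification. Sample size, outcome definitions and analysis model stay as they are.

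Starting on the evening before the listed day is less good. At 15 kg and over it would raise doses on days 4, 7 and 10, which have no assessment in Table 4, and lift those daily totals by 11% (250 vs 225), 17% (350 vs 300) and 11% (500 vs 450).

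Only if the investigators and pharmacy confirm that joint increases are intended should the unconditional rule be removed from the risk paragraph and the phrase about the evening dose in Dose Escalation be limited to the early steps. That is text only and changes no dose.
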